## 9.4.1.3 Intratumoral Injection

Lesions selected for injection must be at least 1.0 cm for solid tumors, and >1.5 cm for lymphoma in the longest diameter, so as to be measureable by RECIST (solid tumors) or Lugano criteria (lymphoma). The maximum size of any injected lesion is 3.0 cm in the longest diameter for both solid tumors and lymphoma. Lymph nodes for injection must be at least 1.5 cm in the short axis for solid tumors and >1.5 cm in the longest diameter for lymphoma.

Investigators will define which lesions are appropriate for E7766 injection. Preference in the initial dose levels will be given to easier to access lesions. Intratumoral injection approaches for lesions that are proximal to major vessels or those deemed to have a risk of bleeding should be discussed in a multidisciplinary setting with regards to safety of the approach in order to avoid a risk of vascular catastrophe and/or inadvertent risk of intravascular systemic injection. Lesions in the vicinity of major vessels with a high risk of bleeding (eg, the common, internal or external carotid arteries or their branches), or other situations with a risk of vascular catastrophe such as tumor-encased large vessels, subcapsular liver lesions, hypervascular tumors, lesions that have been previously irradiated, lesions with macroscopic intravascular tumor invasion (eg, liver lesions with tumor infiltration into the main portal vein, hepatic vein or vena cava) should be excluded from intratumoral injection. To avoid potential risk of bleeding and systemic exposure, Doppler ultrasound guidance is recommended for intratumoral injections with E7766 to ensure that the injection is not carried out within a vessel (Marabelle, et al., 2018). Lesions selected for injections must not have been subjected to any prior intratumoral therapy.

Local (at site of injection) plus or minus systemic analgesic treatments should be anticipated and are recommended to be initiated at least 30 minutes before undertaking intratumoral injection procedure. Skin analgesia at the site of injection can be administered using topical xylocaine (4%) or other local anaesthetic agents. The options for systemic analgesia are recommended to include the full range of analgesia from paracetamol/acetaminophen to opioids, depending on the precise details of the procedure and the subject's underlying symptoms (Marabelle, et al., 2018).

Eisai Confidential Page 67 of 138

The same lesion will be injected at each administration. In the event that the injected lesion shrinks and/or is no longer injectable (ie, no longer accessible, not appropriate for injection, or for other reasons), additional lesions may also be considered for injection and the same guidance for injection of these lesions will apply in terms of accessibility, injectability, and follow-up. The sequence of lesion selection for injection should be agreed in advance by the investigator and treating team. If no other injectable lesions are available, treatment will stop.

Additional guidance for direct and ultrasound/CT guided injection will be provided in a separate manual.

### 9.4.1.4 Management of Cytokine Release Storm

Cytokine release storm (CRS) has been identified as a potential safety risk in immunotherapies, especially drugs that act as agonists for immune activation. Guidance for identification and management is provided in Table 5. IL-6 will be assessed by the site as clinically indicated. For E7766 dose adjustments and interruptions for the management of CRS, refer to Table 4.

Table 5 Management of Cytokine Release Storm and Organ Toxicity

CRS Grade	Sign/Symptom	Management
(CTCAE)		
Grade 1	Fever or Grade 1 organ toxicity	
 
Acetaminophen and hypothermia blanket as needed for fever
 
Ibuprofen if fever is not controlled with above; use with caution or avoid if thrombocytopenic
 
Assess for infection with blood and urine cultures, and chest x-ray
 
Consider antibiotics and filgrastim (if neutropenic)
 
IV fluids as needed
 
Symptomatic management of constitutional symptoms and organ toxicities
 
Consider IL-6 antagonist for persistent (greater than 3 days) or refractory fever
 

Grade 2	Hypotension	
 
IV fluid bolus of 500 – 1,000 mL normal saline; repeat as necessary to maintain SBP greater than 90 mmHg
 
Consider IL-6 antagonist¹ for hypotension refractory to fluid boluses
 
If hypotension persists after two fluid boluses and IL-6 antagonist¹, start vasopressors, transfer patient to ICU, and obtain ECHO
 
In patients at high-risk for severe CRS², if hypotension persists after IL-6 antagonist¹, if there are signs of hypoperfusion³ or if there is rapid deterioration in the opinion of the clinician, may use dexamethasone 10 mg IV every 6 hours
 
Manage fever and constitutional symptoms as in Grade 1 CRS
 

	Hypoxia  Grade 2 organ toxicity	
 
Use supplemental oxygen as needed
 
Use IL-6 antagonist with or without corticosteroids as in hypotension
 
Manage fever and constitutional symptoms as in Grade 1 CRS
 
Manage organ toxicity as per standard guidelines
 
Use IL-6 antagonist with or without corticosteroids as in hypotension
 
Manage fever and constitutional symptoms as in Grade 1 CRS
 

Grade 3	Hypotension	
 
IV fluid boluses as needed as in Grade 2 CRS
 
IL-6 antagonist as in Grade 2 if not administered previously
 
Use vasopressors as needed
 
Transfer patient to ICU and obtain ECHO if not performed already
 
Start dexamethasone 10 mg IV every 6 hours; increase to 20 mg IV every 6 hours
 

Eisai Confidential Page 68 of 138

		T
		if refractory
		Manage fever and constitutional symptoms as in Grade 1 CRS
	Нурохіа	Use supplemental oxygen including high-flow oxygen delivery and non-invasive positive pressure ventilation
		• Use IL-6 antagonist  , corticosteroids as above and supportive care
	Grade 3	Manage organ toxicity as per standard guidelines
	organ toxicity or	• Use IL-6 antagonist  , corticosteroids as above and supportive care
	Grade 4 increased transaminases	Manage fever and constitutional symptoms as in Grade 1 CRS
Grade 4	Hypotension	• IV fluids, IL-6 antagonist  , vasopressors, and hemodynamic monitoring as in
		Grade 3
		High-dose methylprednisolone 
		Manage fever and constitutional symptoms as in Grade 1
	Hypoxia	Mechanical ventilation
		• Use IL-6 antagonist  , high-dose methylprednisolone  and supportive care
	Grade 4	Symptomatic management of organ toxicity as per standard guidelines
	organ toxicity,	• Use IL-6 antagonist  , high-dose methylprednisolone  and supportive care
	excluding	
	increased	
	transaminases	

CRS = cytokine release storm, CTCAE = Common Terminology Criteria for Adverse Events, ECHO = echocardiogram, ICU = intensive care unit, IL-6 = interleukin 6, IV = intravenous, SBP = systolic blood pressure.

- High tumor burden
- Early onset CRS (less than 3 days from cell infusion)
- Co-morbidities (a score of 3 or greater using the Hematopoietic Cell Transplantation Comorbidity Index; for solid tumor patients prior solid tumor will not be counted)

- Decreased urine output (less than 0.5 mL/kg/hour)
- Lactate greater than or equal to 4 mmol/L, rising lactate, and/or poor lactate clearance (less than 10%) despite adequate fluid resuscitation.

Source: Adapted from MD Anderson Cancer Center CAR cell therapy toxicity assessment and management protocol (Teachey, et al., 2016; MD Anderson Cancer Center, 2017).

## 9.4.2 Identity of Investigational Product(s)

#### 9.4.2.1 Chemical Name, Structural Formula of E7766

#### **Standard Text**

Test drug code: E7766Generic name: N/A

• Chemical name: (1R,3R,15E,28R,29R,30R,31R,34R,36R,39S,41R)-29,41-Difluoro-34,39-bis(sulfanyl)-2,33,35,38,40,42-hexaoxa-4,6,9,11,13,18,20,22,25,27-decaaza-34 $\lambda^5$ ,39 $\lambda^5$ -diphosphaoctacyclo [28.6.4.1.1.0.0.0.0]dotetraconta-5,7,9,11,15,19,21,23,25-nonaene-34,39-dione diammonia

Eisai Confidential Page 69 of 138

<sup>1 See Appendix 6 for Interleukin-6 Antagonist and Corticosteroid Dosing Tables.

<sup>2 High risk for CRS includes any of the following:

<sup>3 Signs of hypoperfusion include:

Molecular formula: C24H26F2N10O8P2S2·2NH3
 Molecular weight: 780.66 (746.60, Free Acid)

#### 9.4.2.2 Comparator Drug

Not applicable.

## 9.4.2.3 Labeling for Study Drug

E7766 will be labeled in accordance with text that is in full regulatory compliance with each participating country and will be translated into the required language(s) for each of those countries.

## 9.4.2.4 Storage Conditions

Study drug will be stored in accordance with the labeled storage conditions. Temperature monitoring is required at the storage location to ensure that the study drug is maintained within an established temperature range. The investigator or designee (or if regionally required, the head of the medical institution) is responsible for ensuring that the temperature is monitored throughout the total duration of the study and that records are maintained; the temperature should be monitored continuously by using either an in-house validated data acquisition system, a mechanical recording device, such as a calibrated chart recorder, or by manual means, such that minimum and maximum thermometric values over a specific time period can be recorded and retrieved as required.

## 9.4.3 Method of Assigning Subjects to Treatment Groups

This is an open-label, single-arm study. All subjects who provide signed informed consent to participate in this study and satisfy all eligibility requirements (see Section 9.3) will be assigned to receive E7766. There is no randomization in this study.

## 9.4.4 Selection of Doses in the Study

Refer to Section 9.2 for the rationale for FIH dose selection.

### 9.4.5 Selection and Timing of Dose for Each Subject

Refer to Section 9.4.1.1 for dosing schedule for E7766.

#### 9.4.6 Blinding

This is an open-label study; the treatment will not be blinded.

## 9.4.7 Prior and Concomitant Therapy

All prior medications (including over-the-counter medications) administered 30 days before the first dose of study drug and any concomitant therapy administered to the subject during the course of the study (starting at the date of informed consent) until 90 days after the final dose of study drug or start day of another anticancer therapy, whichever is earlier. If the subject initiates new anticancer therapy within 30 days, then concomitant medications must be collected for 30 days following the last dose of E7766. Additionally, all diagnostic, therapeutic, or surgical procedures relating to malignancy should be recorded. Any medication that is considered necessary for the subject's health and that is not expected to interfere with the evaluation of or interact with E7766 may be continued during the study.

Treatment of complications or AEs, or therapy to ameliorate symptoms (including blood products, blood transfusions, fluid transfusions, antibiotics, and antidiarrheal drugs), may be given at the discretion of the investigator, unless it is expected to interfere with the evaluation of (or to interact with) E7766.

Aspirin, nonsteroidal anti-inflammatory drugs (NSAIDs), and LMWH are permissible but should be used with caution. It is recommended that their LMWH treatment is stopped 24 hours before the intratumoral injection and resumed again 24 hours after the injection. Granulocyte colony-stimulating factor (g-CSF) or equivalent may be used in accordance with American Society of Clinical Oncology (ASCO), institutional, or national guidelines. Erythropoietin may be used according to ASCO, institutional, or national guidelines, but the subject should be carefully monitored for increases in red blood cell counts.

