#### **Exclusion Criteria**

- 1. Other malignancy active within the previous 2 years except for basal or squamous cell skin cancer, superficial bladder cancer, or carcinoma in situ of the cervix or breast that has completed curative therapy.
- 2. Subjects with any active autoimmune disease (Appendix 5) or a documented history of autoimmune disease, except for subjects with vitiligo or resolved childhood asthma/atopy.
- 3. Known human immunodeficiency virus (HIV) infection.
- 4. Active infection requiring therapy, including known positive tests for Hepatitis B surface antigen or Hepatitis C ribonucleic acid (RNA).
- 5. Major surgery within 4 weeks before the first dose of study drug.
- 6. Concurrent medical condition requiring the use of immunosuppressive medications or immunosuppressive doses of systemic medications, such as steroids or absorbed topical steroids (doses >10 mg/day prednisone or equivalent).
- 7. Brain metastases that are untreated or in the posterior fossa or involve the meninges. Subjects with stable or progressing brain metastases (except in the posterior fossa or involving the meninges) previously treated with brain stereotactic radiotherapy (SRT), whole-brain radiotherapy (WBRT) and/or surgery are allowed as long as the subject is asymptomatic neurologically and does not require immediate local intervention (radiotherapy and/or surgery). In addition, subjects must be off immunosuppressive doses of systemic steroids (>10 mg/day prednisone or equivalent) for at least 4 weeks before study drug administration.

Eisai Confidential Page 13 of 138

- 8. Prolongation of corrected QT (QTcF) interval to >450 msec for males and females, when electrolytes balance is normal
- 9. Significant cardiovascular impairment: history of congestive heart failure greater than New York Heart Association (NYHA) Class II, uncontrolled arterial hypertension, unstable angina, myocardial infarction, or stroke within 6 months of the first dose of study drug, or cardiac arrhythmia requiring medical treatment (including oral anticoagulation).
- 10. Subjects on oral anticoagulants including low dose aspirin. To meet eligibility, these subjects can be switched to receive preventive dose of low molecular weight heparin (LMWH). It is recommended that their LMWH treatment is stopped 24 hours before the intratumoral injection and resumed again 24 hours after the injection.

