#### 9.1.3.2 Treatment Phase

Subjects whose screening assessments and evaluations are completed and reviewed by the principal investigator and who continue to meet all of the inclusion/exclusion criteria will enter the Treatment Phase.

Eisai Confidential Page 57 of 138

The Treatment Phase will extend from the start of study drug administration in Cycle 1 and will last for 1 treatment cycle of 21 days in the Dose Escalation part and 6 cycles in the Dose Expansion part. At the end of the Treatment Phase subjects will continue to the Extension Phase.

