#### 9.3.2 Exclusion Criteria

Subjects with any of the following criteria will be excluded from this study:

- 1. Other malignancy active within the previous 2 years except for basal or squamous cell skin cancer, superficial bladder cancer, or carcinoma in situ of the cervix or breast that has completed curative therapy.
- 2. Subjects with any active autoimmune disease (Appendix 5) or a documented history of autoimmune disease, except for subjects with vitiligo or resolved childhood asthma/atopy.
- 3. Known human immunodeficiency virus (HIV) infection.
- 4. Active infection requiring therapy, including known positive tests for Hepatitis B surface antigen or Hepatitis C ribonucleic acid (RNA).
- 5. Major surgery within 4 weeks before the first dose of study drug.
- 6. Concurrent medical condition requiring the use of immunosuppressive medications or immunosuppressive doses of systemic medications, such as steroids or absorbed topical steroids (doses >10 mg/day prednisone or equivalent).
- 7. Brain metastases that are untreated or in the posterior fossa or involve the meninges. Subjects with stable or progressing brain metastases (except in the posterior fossa or involving the meninges) previously treated with brain stereotactic radiotherapy (SRT), whole-brain radiotherapy (WBRT) and/or surgery are allowed as long as the subject is asymptomatic neurologically and does not require immediate local intervention (radiotherapy and/or surgery). In addition, subjects must be off immunosuppressive doses of systemic steroids (>10 mg/day prednisone or equivalent) for at least 4 weeks before study drug administration.
- 8. Prolongation of corrected QT (QTcF) interval to >450 msec for males and females, when electrolytes balance is normal.

Eisai Confidential Page 62 of 138

- 9. Significant cardiovascular impairment: history of congestive heart failure greater than New York Heart Association (NYHA) Class II, uncontrolled arterial hypertension, unstable angina, myocardial infarction, or stroke within 6 months of the first dose of study drug, or cardiac arrhythmia requiring medical treatment (including oral anticoagulation).
- 10. Subjects on oral anticoagulants including low dose aspirin. To meet eligibility, these subjects can be switched to receive preventive dose of low molecular weight heparin (LMWH). It is recommended that their LMWH treatment is stopped 24 hours before the intratumoral injection and resumed again 24 hours after the injection.

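### Low-dose aspirin bars entry under Exclusion 10, but Section 9.4.7 permits aspirin during treatment with no dose limit and no hold around injections or the Cycle 2 Day 1 biopsy

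*Protocol*

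**What the plan says.** **At entry.** Exclusion Criterion 10 (Synopsis and Section 9.3.2) excludes "Subjects on oral anticoagulants including low dose aspirin". It offers one explicit route back: "To meet eligibility, these subjects can be switched to receive preventive dose of low molecular weight heparin (LMWH"). It recommends holding LMWH for 24 hours on each side of an injection. Section 9.1.3.2 applies the criteria at the start of treatment: subjects "who continue to meet all of the inclusion/exclusion criteria will enter the Treatment Phase".

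**During treatment.** Section 9.4.7 states: "Aspirin, nonsteroidal anti-inflammatory drugs (NSAIDs), and LMWH are permissible but should be used with caution". The next sentence repeats the hold from Exclusion 10, again for LMWH alone: "It is recommended that their LMWH treatment is stopped 24 hours before the intratumoral injection and resumed again 24 hours after the injection".

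**Procedures after entry.** Injections are given on Days 1, 8 and 15 of Cycle 1, then on Day 1 of each 3-week cycle. Section 9.5.1.4.2 and Table 7 footnote q require a biopsy on Cycle 2 Day 1, in the injection session and after the drug is given. The injected lesion is sampled and, where available, one non-injected lesion.

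**The concern.** The protocol treats low-dose aspirin as reason enough to refuse entry, then lists aspirin as allowed from the moment treatment begins. A subject who stops aspirin, or changes to LMWH, in order to qualify is not prevented from going back to it.

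The protocol does not say why Exclusion 10 exists. Procedural bleeding is the natural inference: the LMWH hold is tied to the injection, and Section 9.4.1.3 says "To avoid potential risk of bleeding and systemic exposure, Doppler ultrasound guidance is recommended for intratumoral injections with E7766". If that is the reason, it does not end at entry. It recurs at every injection, and the Cycle 2 Day 1 session adds a biopsy to the injection.

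There may also be a consequence for dose finding, which is inference and cannot be quantified here. Under Table 1, one DLT among two subjects at a dose means de-escalation, with an allowance at the lowest dose. A Cycle 1 bleed to which aspirin contributed, if judged a drug-related DLT, could change the dose path.

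**Working it through.** The plan gives no figure to reproduce, and the point is mainly textual. The check sets the rules side by side, looks for an aspirin rule elsewhere, and counts the procedures involved.

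**1. Entry rule against treatment rule**

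| Item | Exclusion 10 | Section 9.4.7 |
|---|---|---|
| Aspirin | Low-dose use excludes | Permitted, with caution |
| Aspirin dose limit | Not applicable | None |
| Aspirin hold around injection | Not applicable | None |
| LMWH | Preventive dose allowed | Permitted, with caution |
| LMWH hold around injection | 24 h before and after, recommended | Same, recommended |

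The LMWH part of the entry arrangement is carried into treatment. The aspirin part is replaced by a permission. LMWH, the offered substitute, has a specific hold; aspirin has none.

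**2. Search for an aspirin rule elsewhere in the visible text**

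- Prohibited therapies (Synopsis and Section 9.4.7.2): none.
- Injection guidance (Section 9.4.1.3): lesion selection, Doppler guidance and analgesia, but no aspirin rule.
- Biopsy text (Section 9.5.1.4.2 and Table 7 footnote q): none.
- Laboratory review before dosing at the start of each cycle (Section 9.5.1.5.3; Table 6 includes platelets and INR): a continuing control, but not a rule on aspirin use.

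**3. Comparison with another entry drug restriction**

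Immunosuppressive steroid doses are restricted at entry (Inclusion 8, Exclusion 6), and Section 9.4.7.2 prohibits systemic steroids on treatment. That restriction is carried forward; the aspirin restriction is not, and no reason is given.

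**4. Procedures after entry**

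- Up to and including Cycle 2 Day 1: 3 injections in Cycle 1 + 1 in Cycle 2 = 4. After the first: 4 − 1 = 3. The biopsy shares the session of the fourth injection, so it adds no session.
- Through Cycle 6: 3 in Cycle 1 + 5 in Cycles 2 to 6 = 8. After the first: 8 − 1 = 7.
- Each later 3-weekly injection adds one more.

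These counts show how much of the schedule falls under 9.4.7. They do not measure bleeding risk.

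**The case against.** **The two passages can both be followed.** This is correct, and no contradiction is claimed. The defect is that an express permission undoes an entry restriction.

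**The evident plan is that switched subjects stay on LMWH.** Section 9.4.7 speaks of resuming LMWH after the injection, which fits that plan. It supports the likely intent, but the section does not require it and names aspirin as allowed.

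**Section 9.4.7 may mean symptomatic use, since it lists aspirin beside NSAIDs.** This is plausible. But no purpose or dose is given, so low-dose antithrombotic aspirin is covered too. A phrase stating the purpose would help, yet would still leave no hold.

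**A rule may sit where it cannot be seen.** One prohibited-therapy bullet is redacted, Section 9.4.7.1 shows no text, Appendix 7 is not shown, and the protocol says "Additional guidance for direct and ultrasound/CT guided injection will be provided in a separate manual". This limit stands. A hidden prohibition would conflict with the express permission, so 9.4.7 would still need correcting. A hold in the manual would be compatible and would close part of the gap, but 9.4.7 should then refer to it.

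**Bleeding is managed in other ways.** High-risk lesions are excluded from injection, and Doppler guidance is recommended throughout. This is true and lowers the stakes, but none of it governs aspirin.

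**The counts only restate the schedule.** This is fair. Exclusion 10 also states no aspirin washout, so even its cover of the first injection is limited. The pretreatment biopsy, taken during screening, lies outside the counts.

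**Removing all aspirin goes beyond a rule about low-dose aspirin, while NSAIDs stay.** The entry wording can be read as aspirin even at low dose, so the change does not clearly exceed it. Exclusion 10 does not name NSAIDs, and Table 5 relies on one of them for Grade 1 cytokine release: "Ibuprofen if fever is not controlled with above; use with caution or avoid if thrombocytopenic".

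**Conclusion.** The concern holds. In the visible text, low-dose aspirin excludes a subject at entry, yet aspirin is permitted on treatment with no dose limit and no hold around injections or the Cycle 2 Day 1 biopsy. The looser rule covers 3 of the 4 planned injections up to and including the biopsy session, and 7 of 8 if treatment runs through Cycle 6.

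This rests on two assumptions: that procedural bleeding is the reason for Exclusion 10, and that no aspirin hold exists in the redacted text or the injection manual. The documents do not say how many subjects have an indication for aspirin, so the number affected cannot be estimated. No stated statistical figure changes.

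The change should be made, with medium confidence. SAP Sections 3.2.2 and 7 report that escalation ended early and no expansion subjects will be enrolled, which reduces the remaining exposure. Injections may still continue: the data cutoff may precede the last discontinuation (SAP Section 5), and Protocol Section 9.1.3.3 lets benefiting subjects stay on E7766 after study termination.

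**What to change.** In Section 9.4.7:

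- Remove aspirin from the list of permissible drugs, and state that the Exclusion 10 restriction on aspirin continues while intratumoral injections and biopsies are ongoing.
- Name preventive-dose LMWH as the alternative where antithrombotic cover is needed, with the recommended hold 24 hours before and after each injection, including the Cycle 2 Day 1 injection and biopsy session.
- Add that a new indication for aspirin arising on study is to be discussed with the sponsor before the next injection or biopsy.

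Leave the NSAID wording as it is.

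**Cost.** This is a short amendment, but it bears on safety, so Section 11.1 requires submission to authorities and IRB/IEC approval. It could be bundled with another amendment if one is planned; after the early stop, none is visible. Some subjects would stay on LMWH for longer, and a new aspirin indication would need a conversation before the next procedure. How many subjects that involves is unknown.
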